## 1.0 Objectives

Tobacco use continues to be a leading cause of preventable disease and early death. The majority of people who smoke are interested in quitting and attempt to quit each year, but successfully quitting can be challenging for many reasons. In particular, smoking cessation can be especially hard when smokers are dealing with unmet social and health needs and areas of financial stress, which are disproportionately experienced by low-income smokers. In this study, we extend previous research showing that food insecurity is independently associated with higher odds of smoking and can act as a barrier to quitting smoking. Therefore, we design and test a 12-week intervention to assist food-insecure smokers who are ready and willing to make a quit attempt. Beyond providing the quit assistance that smokers normally receive, the research seeks to address food insecurity in the short-term by providing economic food assistance during the quit attempt that will help to meet food needs. We will adapt a patient navigation model in which a designated study navigator can help bridge resources and referrals related to tobacco cessation and food access, and provide economic food assistance based on individualized needs. We will recruit 60 participants for a 12-week study, and all participants will be smokers who are ready to quit and have recently experienced food insecurity. All participants will receive quit assistance and information on local food assistance resources, and a monthly check-in from the navigator. In addition, half of the participants (n=30) will be randomly assigned to the intervention arm, and will receive economic food assistance to partially meet their food needs and reduce food insecurity during the cessation attempt. We will assess feasibility and acceptability of the intervention, and preliminary outcomes related to smoking cessation, such as the number of quit attempts lasting 24 hours or more and the longest length of abstinence from tobacco. By conducting this study, we seek to understand whether this type of intervention is feasible to conduct, and acceptable to those who participate. The study findings will serve as the basis of future research on understanding and addressing tobacco-related and food insecurity-related health disparities. Our main research question is whether addressing food insecurity specifically during a smoking cessation attempt is helpful for increasing quitting success rates.

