### 3.0 Study Endpoints

As a pilot study, primary endpoints are feasibility and acceptability of the intervention. Secondary endpoints are the number of quit attempts lasting 24 hours or more over the past 3 months, and the longest length of smoking abstinence in days over the past 3 months.

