### 5.3 Risk Minimization Procedures and Data Collection Materials

To minimize risks related to annoyance or discomfort over study-related assessments (i.e., surveys and check-in calls with the study navigator), we will inform all potential participants that assessments may ask personal questions, and the estimated duration of the assessments. Participants have the option to skip any question that they do not wish to answer in the surveys. To minimize risks related to potential breach of confidentiality of research participants, we will use secure research systems, namely REDCap, for store any research-related information. To minimize any unforeseeable economic risks (e.g., potential theft of the VISA gift cards), we will ask all participants to keep their participation in this study private (such as not posting on social media about participation). All data collection materials include an Eligibility Script, a Baseline/Follow-up Survey, a Call Log, and a Qualitative Interview Document. All of these sources are attached in the IRB submission.

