## 6.0 Inclusion and Exclusion Criteria

### 6.1 Screening Process

Participant eligibility will be determined using a screening questionnaire, by the research coordinator. Prior to administering the eligibility questions, all potential participants will be notified that there are specific inclusion criteria for the study, and not everyone will qualify for the study. Potential participants will be notified after the end of the screening questionnaire whether they are eligible or ineligible based on their responses. In some cases, it is possible that eligibility may not be readily apparent. In those cases, potential participants will be informed that their responses will be reviewed by the study PI, and they will be followed up in the next few days.

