### 6.2 Inclusion and Exclusion Criteria

Inclusion:

- Aged 21 or older
- Current tobacco smoker, defined as having smoked daily over the past 7 days
- Willing to make a serious quit attempt in the next 30 days ("Yes" to "In the next 30 days, are you willing to try quitting smoking for at least 24 hours?")
- Considered food insecure, based on past 30-day screening using the 2-item Hunger Vital Sign, or by virtue of having visited a food pantry in the past 30 days
- A reliable telephone number and a local mailing address where participant can be reached during the duration of the study

Exclusion:

- Aged 20 or younger
- Non-smoker, or a current tobacco smoker who did not smoke daily over the past 7 days
- Not interested in quitting at this time, assessed by unwillingness to make a serious quit attempt in the next 30 days ("No" to "In the next 30 days, are you willing to try quitting smoking for at least 24 hours?")
- Did not recently experience food insecurity, based on past 30-day screening using the 2-item Hunger Vital Sign, or has not visited a food pantry in the past 30 days
- Does not have a reliable telephone number and a local mailing address where participant can be reached during the duration of the study

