### 7.3 Methods Used to Identify Potential Participants

We will use the electronic health record (EHR) to prescreen potential participants for this study. Potential participants will comprise of current MetroHealth patients from a total of 7 MetroHealth sites within Cuyahoga county. We will use the EHR to prescreen for age (21 years or older), smoking status as documented in the EHR (documented as currently smoking), and food insecurity status (documented as food insecure based on social determinants of health screening conducted during the most recent visit). Using this list, we will send out a recruitment packet in the mail, consisting of a 1-page study flyer with key information and a copy of the informed consent document, in the form of a non-return cover memo. The flyer will instruct potential participants to contact the study team by telephone for further information about the study, and to see if they qualify.

As needed and based on recruitment rate, the research team will also make telephone calls to follow-up with potential participants, after having sent recruitment letters (i.e., there is no “cold” calling without sending letters beforehand). Using the prescreened list of individuals, we will randomly follow up with individuals on the list until we reach the enrollment target for the wave (n=15-20 enrolled in each wave; 3-4 enrollment waves; 60 participants in total will be recruited for this study).

To identify potential participants for the end-of-study qualitative interviews, we will attempt to contact everyone who would be eligible based on their intervention assignment and completion of the protocol.

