## 11.0 Data Analysis Plan

As a pilot study, the primary outcomes pertain to the assessment of feasibility and acceptability, and to derive preliminary estimates of tobacco cessation measures and food security status. We will conduct t-tests and chi-square tests to explore group differences. Feasibility will be assessed by examining the number of participants screened, percent eligible to participate, refusal rate, and attrition rate between baseline and 12-week follow-up. We will examine participants' utilization of resources related to tobacco cessation and food assistance, to examine feasibility of the navigation model. We will gain feedback from the navigator regarding the process of providing referrals and individualized food assistance. We will evaluate acceptability through open-ended questions to elicit participant feedback regarding their perceptions of helpfulness of food assistance in meeting food needs, helpfulness of food assistance specifically during cessation attempt, and additional barriers and facilitators to making a quit attempt or staying quit.

Qualitative interviews will be transcribed and analyzed using inductive and deductive coding process.

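### The food-insecurity exclusion in section 6.2 is not the negation of the inclusion, so a person who meets only one of the two conditions is both included and excluded

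*Combined protocol and SAP*

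**What the plan says.** The inclusion list in section 6.2 of the combined protocol and SAP offers two routes to qualifying on food insecurity, each with a 30-day window: "Considered food insecure, based on past 30-day screening using the 2-item Hunger Vital Sign, or by virtue of having visited a food pantry". Either route is enough. The corresponding exclusion rejects a person who did not recently experience food insecurity on screening "using the 2-item Hunger Vital Sign, or has not visited a food pantry in the past 30 days".

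Four other places bear on the rule:

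- Section 1.0 describes the target population in general terms: "all participants will be smokers who are ready to quit and have recently experienced food insecurity".
- Sections 5.2 and 7.3 build the contact list from health records of patients "documented as food insecure based on social determinants of health screening conducted during the most recent visit". Neither mentions pantry use.
- Section 6.1 has the coordinator decide eligibility with a screening questionnaire and provides for review by the principal investigator: "In some cases, it is possible that eligibility may not be readily apparent".
- Section 5.3 states "All data collection materials include an Eligibility Script" and places these materials with the IRB submission. The script's text is not in the documents.

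On use of the result, section 3.0 says that "primary endpoints are feasibility and acceptability of the intervention". Section 11.0 assesses feasibility by "examining the number of participants screened, percent eligible to participate, refusal rate" and attrition to week 12.

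**The concern.** An exclusion that restates an inclusion should reject exactly the people whom the inclusion does not admit. This one also rejects people whom the inclusion admits.

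The affected case is foreseeable. The contact list is selected on recorded food insecurity and not on pantry use, so some callers can be expected to screen positive without having been to a pantry in the past month. The inclusion bullet enrols such a caller and the exclusion bullet turns the same caller away.

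Two things are at stake. If the exclusion is applied as worded, the sample narrows to food-insecure smokers who also use pantries, a narrower group than the one section 1.0 describes. If it is applied unevenly between callers or enrolment waves, the percentage eligible mixes two rules. It is then hard to interpret and hard to carry into the later research that section 1.0 says this pilot will inform.

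**Working it through.** **Inputs.** Let A be a positive 30-day Hunger Vital Sign screen and B a pantry visit in the past 30 days. From section 6.2:

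- Inclusion: A or B.
- Exclusion as worded: (not A) or (not B).
- True negation of the inclusion: (not A) and (not B).

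**Truth table.**

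| A | B | Included | Excluded as worded | Excluded by true negation | Result as worded |
|---|---|---|---|---|---|
| yes | yes | yes | no | no | eligible |
| yes | no | yes | yes | no | contradiction |
| no | yes | yes | yes | no | contradiction |
| no | no | no | yes | yes | ineligible |

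Two of the four cells conflict as worded. With the true negation, none does. Applying both bullets literally leaves only the first row, so enrolment would require A and B.

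**Alternative parse.** The pantry clause could be read as a second ground for concluding that the person was not food insecure. That changes nothing: lacking a pantry visit would still be enough to exclude.

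**Effect on the percentage eligible.** The plan gives no percentage eligible and no rates for A or B, so there is no figure to reproduce. In general:

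- Share passing this criterion under the inclusion rule: P(A or B) = P(A) + P(B) − P(A and B).
- Share passing if the exclusion is also enforced literally: P(A and B).
- Gap: P(A) + P(B) − 2 × P(A and B), the share with exactly one condition.

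Equivalently, let q be the share meeting both conditions among people who pass the inclusion rule and all other criteria. The literal percentage eligible is then q times the inclusion-rule percentage. At q = 1 nothing changes; as q approaches 0 almost nobody qualifies.

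**Illustration only.** The rates below are assumptions, and A and B are taken as independent.

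| P(A) | P(B) | P(A and B) | P(A or B) | Gap (percentage points) |
|---|---|---|---|---|
| 0.95 | 0.70 | 0.95 × 0.70 = 0.665 | 0.95 + 0.70 − 0.665 = 0.985 | 32 |
| 0.70 | 0.70 | 0.70 × 0.70 = 0.49 | 0.70 + 0.70 − 0.49 = 0.91 | 42 |
| 0.90 | 0.30 | 0.90 × 0.30 = 0.27 | 0.90 + 0.30 − 0.27 = 0.93 | 66 |
| 0.95 | 0.20 | 0.95 × 0.20 = 0.19 | 0.95 + 0.20 − 0.19 = 0.96 | 77 |

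Over assumed P(A) from 0.70 to 0.95 and P(B) from 0.20 to 0.70, the gap runs from 32 to 77 points under independence. It depends heavily on overlap: if both rates are 0.70 and the same people meet both conditions, the gap is 0.70 + 0.70 − 2 × 0.70 = 0. These figures show that the wording can matter. They do not estimate how much it does.

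**The case against.** The strongest reply is that context shows what was meant. The inclusion bullet treats a pantry visit as sufficient by itself, which would be pointless if both conditions were required. The exclusion bullet opens by describing people who were not food insecure, and someone with one condition is food insecure by the inclusion definition. The general aim in section 1.0 and the record-based prescreen point the same way. This stands as evidence of intent: the second 'or' was probably meant as 'nor'. It remains an inference, and no section states it as the rule.

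It can also be said that the practical effect depends on the eligibility script. If the script accepts either answer, callers are classified correctly whatever section 6.2 says. That is true, and it limits what can be claimed. The script cannot be seen, so it cannot be assumed either to correct the wording or to repeat it.

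Review by the principal investigator is a partial safeguard, since one reviewer makes uneven application less likely. But section 6.1 gives that reviewer no tie-break for a person with one condition, and a coordinator applying the exclusion literally might not see the case as unclear.

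Finally, the other four exclusion bullets are mirrors of their inclusions in intent but are loosely drafted. An unsure answer on willingness to quit fits neither quoted response, and the telephone-and-address exclusion can be read as lacking either item or lacking both. So the contrast with the other bullets should not be pressed hard. It does not remove the conflict in the food-insecurity pair.

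**Conclusion.** The concern holds. Section 6.2 contradicts itself for people who meet exactly one of the two food-insecurity conditions, which is two of the four possible combinations, and nothing in the documents resolves the conflict. This follows from the wording and needs no numerical assumption.

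No size is claimed for the effect on the percentage eligible. It lies anywhere between no change and near-total loss of eligibility, according to the unknown overlap, and it arises only if the exclusion is applied literally or inconsistently.

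The consequences are bounded. The plan states no feasibility threshold, so no decision is shown to change. Randomisation follows screening, so the comparison between arms is not biased. The target of 60 participants and the planned tests are unaffected. What remains is an ambiguous eligibility rule that feeds a measure of a primary endpoint. It should be corrected, although it does not threaten the trial.

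**What to change.** Reword the exclusion so that it rejects only a person who neither screens positive on the Hunger Vital Sign nor has made a pantry visit, both over the past 30 days. Alternatively, delete the bullet, since the inclusion already sets the rule.

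Then check that the eligibility script applies the inclusion rule, and report the percentage eligible under that single rule. If anyone has already been screened, review whether callers with only one condition were turned away and state how they were counted.

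The cost is a minor wording amendment to one bullet and a check of the script. No participants, procedures or analyses are added.

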## 7.0 Recruitment Methods

### 7.1 When, Where, and How Potential Participants are Recruited

Recruitment will be conducted by telephone, and there will be no face-to-face visits as part of this study. The study coordinator will use a script to inform participants about the research study being conducted, to assess interest in participating, and to conduct an eligibility screening for interested participants. Individuals will be informed prior to the eligibility screening that not all people who are interested will qualify for the study based pre-determined eligibility criteria. For those who are interested, meet eligibility criteria, and wish to participate, the coordinator will go over the consent form, give the opportunity to ask any questions, and after all questions have been addressed, will collect verbal consent.

### 7.3 Methods Used to Identify Potential Participants

We will use the electronic health record (EHR) to prescreen potential participants for this study. Potential participants will comprise of current MetroHealth patients from a total of 7 MetroHealth sites within Cuyahoga county. We will use the EHR to prescreen for age (21 years or older), smoking status as documented in the EHR (documented as currently smoking), and food insecurity status (documented as food insecure based on social determinants of health screening conducted during the most recent visit). Using this list, we will send out a recruitment packet in the mail, consisting of a 1-page study flyer with key information and a copy of the informed consent document, in the form of a non-return cover memo. The flyer will instruct potential participants to contact the study team by telephone for further information about the study, and to see if they qualify.

As needed and based on recruitment rate, the research team will also make telephone calls to follow-up with potential participants, after having sent recruitment letters (i.e., there is no “cold” calling without sending letters beforehand). Using the prescreened list of individuals, we will randomly follow up with individuals on the list until we reach the enrollment target for the wave (n=15-20 enrolled in each wave; 3-4 enrollment waves; 60 participants in total will be recruited for this study).

To identify potential participants for the end-of-study qualitative interviews, we will attempt to contact everyone who would be eligible based on their intervention assignment and completion of the protocol.

### 7.4 Materials Used to Recruit Participants

We will send out a recruitment packet in the mail, consisting of a 1-page study flyer with key information and a copy of the informed consent document, in the form of a non-return cover memo. The flyer will instruct potential participants to contact the study team by telephone for further information about the study, and to see if they qualify. The study coordinator will use an eligibility script to inform participants about the research study being conducted, to assess interest in participating, and to conduct an eligibility screening for interested participants.

To recruit potential participants for the end-of-study qualitative interviews, we will send an invitation letter and a separate informed consent form as a non-return cover memo.

### 7.5 Amount and Timing of Participant Payments

Participants can receive up to \$105 for participation in the research study, specifically for their time in completing the baseline telephone survey (\$20) and the 12-week telephone survey (\$35, as increased incentive to complete the follow-up survey), and the post-intervention qualitative interview (\$50, as increased incentive to participate in the interview). These will be paid as a separate VISA gift card each time the participant completes the survey, and will be sent by mail.

## 8.0 Withdrawal of Participants

Participants will be removed from the study for any significant medical events, such as hospitalization, or any significant legal events, such as incarceration. Participant non-compliance with research can also be a reason for removing a participant from the study.

## 9.0 Risks to Participants

Breach of confidentiality is a potential risk associated with this study; however, this risk will be minimized via secure storage of the records. Feeling uncomfortable answering questions is a potential risk for this study; however, this risk will be minimized by allowing participants to skip any questions they do not wish to answer.

## 10.0 Potential Benefits to Participants

For participants in either group, a potential benefit to participants is that they have several opportunities to connect with a study navigator who can provide them with useful/relevant information and referrals for tobacco cessation and food assistance.

For participants in the intervention group, a potential benefit of participating in the research is that they may experience short-term relief from food insecurity while they are undergoing a smoking cessation attempt.

## 11.0 Data Analysis Plan

As a pilot study, the primary outcomes pertain to the assessment of feasibility and acceptability, and to derive preliminary estimates of tobacco cessation measures and food security status. We will conduct t-tests and chi-square tests to explore group differences. Feasibility will be assessed by examining the number of participants screened, percent eligible to participate, refusal rate, and attrition rate between baseline and 12-week follow-up. We will examine participants' utilization of resources related to tobacco cessation and food assistance, to examine feasibility of the navigation model. We will gain feedback from the navigator regarding the process of providing referrals and individualized food assistance. We will evaluate acceptability through open-ended questions to elicit participant feedback regarding their perceptions of helpfulness of food assistance in meeting food needs, helpfulness of food assistance specifically during cessation attempt, and additional barriers and facilitators to making a quit attempt or staying quit.

Qualitative interviews will be transcribed and analyzed using inductive and deductive coding process.

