### 5.0 Procedures Involved

#### 5.1 Study Design (Overview)

For most participants, the full length of participation is about 2.5-3 hours spread across 13 weeks (intervention is 12 weeks, and an additional week is included as pre-intervention baseline). For a small proportion of participants (n=8-10) who agree to participate in an end-of-study qualitative interview to share their experiences of the study, the full length of participation is about 2.5-3.5 hours.

1. Telephone conversation to discuss study, assess interest and eligibility, answer participant questions, and provide instructions on consent process (30 minutes)
2. Receive consent form via mail. Prior to randomization, complete a baseline assessment via telephone/online survey (30-45 minutes)
3. At week 1 post-randomization, connect with study navigator by telephone to receive information and referrals about tobacco cessation and food assistance (30 minutes)
- 3a. Participants in the intervention arm will receive instructions about funds (5-10 minutes)
4. Week 4 post-randomization, check-in call with study navigator (10-15 minutes) 4a. Participants in the intervention arm receive additional funds (0-1 minute required for participant)
5. Week 8 post-randomization, check in call with study navigator (10-15 minutes)
- 5a. Participants in the intervention arm receive additional funds (0-1 minute required for participant)
6. Week 12 post-randomization, follow-up assessment (30-45 minutes)
7. Post-intervention qualitative interviews (30-45 minutes)

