**RANDOMIZATION, ALLOCATION:** After the baseline telephone (or online) survey is completed, participants will be randomized in the Intervention arm or the Control arm with a 50/50 chance to be randomized in either arm. The study analyst who has no contact with participants will use a computer-generated random number table to assign participants. In either arm, in Week 1 of the study, all participants will be connected to receive usual care for tobacco cessation, based on their preferences. In either arm, the study navigator (a community health worker) will review participant responses from the baseline telephone survey and reach out to all participants by telephone. This conversation may involve referrals to the tobacco quitline, referrals to counseling/classes offered at MetroHealth or in the community (such as Freedom from Smoking classes), nicotine replacement therapy and/or pharmacotherapy as prescribed by their primary care provider. The study navigator will provide linkages and information to the services available to the participant, which will be documented in a semi-structured call log, and used as the basis of following up on use of tobacco cessation services in subsequent telephone check-ins in Week 4 and Week 8.

In either arm, participants also receive information from the study navigator about local food assistance resources available to them, such as a list of food pantries and community meal sites and eligibility information about federal food assistance programs. Provision of this information will also be documented by a semi-structured call log, and will be used as the basis of following up on food assistance resources in subsequent check-ins in Week 4 and Week 8. Information about tobacco cessation and food assistance resources are provided by telephone and/or in writing, which is within the scope of work for a community health worker.

In the Intervention arm only, participants will receive economic food assistance to meet their individual food and grocery needs during the cessation attempt/study period. This is provided on a monthly basis (3 times during the 12 weeks of the study) during Week 1, Week 5, and Week 9.

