## 5.4 Type of Data Collected and How Data is Obtained

We are collecting both existing and prospective data. Existing data are collected using electronic health records to ascertain potential participants' age, smoking status, and food insecurity screening status. Prospective data are obtained through a baseline and 12-week follow-up survey, collected through REDCap (survey-administered telephone survey, or self-completed survey), and through semi-structured telephone call logs kept by the study navigator.

For end-of-study qualitative interviews, the interviews will be audio-recorded and transcribed verbatim.

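### Section 11 leaves the arm comparisons unadjusted; if the survey asks the two recall endpoints at baseline, adjusting for them is a cheap but small gain in precision (optional)

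*Combined protocol and SAP*

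**What the plan says.** Section 11.0 gives the whole plan for comparing arms in one sentence: "We will conduct t-tests and chi-square tests to explore group differences". No section names a regression model, a covariate or a change score. The same section gives as an aim "to derive preliminary estimates of tobacco cessation measures and food security status", and Section 1.0 says the findings are to support later research.

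Section 3.0 defines two numeric endpoints recalled over three months: "Secondary endpoints are the number of quit attempts lasting 24 hours or more over the past 3 months", and the longest abstinence in days.

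On timing, Section 5.1 says: "Prior to randomization, complete a baseline assessment via telephone/online survey". Section 5.2 agrees: "After the baseline telephone (or online) survey is completed, participants will be randomized in the Intervention arm or the Control arm". Section 5.4 adds: "Prospective data are obtained through a baseline and 12-week follow-up survey". Section 5.3 lists the instruments: "All data collection materials include an Eligibility Script, a Baseline/Follow-up Survey, a Call Log, and a Qualitative Interview Document". The same section also says: "Participants have the option to skip any question that they do not wish to answer in the surveys".

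**The concern.** Naming the baseline and follow-up survey as one instrument suggests that the same items may be asked twice. If so, each participant has a pre-randomisation value of each recall endpoint, and the planned comparison does not use it. A baseline value that predicts the week-12 value removes some of the between-person variation from the arm comparison, with no extra recruitment or data.

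What is at stake is the width of the intervals that a later trial would plan from. Bias and the validity of the tests are not in question. Section 11.0 also promises estimates but names only tests, so as written it does not commit to reporting a difference with an interval.

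**Working it through.** The plan gives no SD, effect size, power or correlation, so it has no figure to reproduce. Results are in SD units.

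**Inputs.** N = 60, 30 per arm (Section 1.0). The correlation r between baseline and week 12 is assumed. A 20% loss, leaving 24 per arm, is also assumed, because the plan treats attrition as an outcome and gives no rate.

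**Formulas.**
- Unadjusted half-width = t(0.975, N−2) × √(4/N).
- Variance ratio after adjusting for one covariate = (1 − r²) × (1 + 1/(N−4)).
- Adjusted half-width = t(0.975, N−3) × √(4/N × ratio).
- Equivalent N = N / ratio.

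**30 per arm.** Unadjusted: 2.002 × √(4/60) = 2.002 × 0.2582 = 0.517.

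| r (assumed) | Variance ratio | Half-width | Equivalent N |
|---|---|---|---|
| 0 | 1 × 1.018 = 1.018 | 0.522 | 59 |
| 0.2 | 0.96 × 1.018 = 0.977 | 0.511 | 61 |
| 0.3 | 0.91 × 1.018 = 0.926 | 0.498 | 65 |

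The two widths are equal at r of about 0.14.

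**24 per arm.** 0.581 unadjusted; adjusted 0.588, 0.576 and 0.561 at r = 0, 0.2 and 0.3.

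**Skewed outcomes.** The two endpoints will probably be skewed, so the formula was checked by simulation with assumed distributions (6,000 runs per setting, 30 per arm, HC2 robust standard errors). Interval width relative to the t interval was 1.01 at r = 0, 0.98–0.99 at r = 0.13–0.21 and 0.94–0.97 at r = 0.24–0.34. HC2 coverage was 94.5–95.9% with no arm effect and 94.1–95.5% with one. The t-test covered 94.4–95.5% with an arm effect. HC3 gave less favourable widths: 1.03–1.04, 1.01–1.02 and 0.97–1.00.

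**How informative could the baseline be?** Section 6.2 requires daily smoking over the past 7 days. Section 2.1 says 55% of smokers tried to quit for a day or more within 12 months. In an average 3 months that implies:
- at least 0.55/4 = 13.75% (about 8 of 60);
- at a constant rate, 1 − 0.45^(1/4) = 18.1% (about 11 of 60);
- at most 55% (33 of 60).

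Participants willing to quit may differ. With 18% non-zero baseline counts, simulated r falls from 0.21 and 0.34 to 0.17 and 0.29, and the HC2 width ratios are 0.99 and 0.96.

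**Unequal arms.** Section 5.2 describes a random number table and no blocking. If allocation is simple, a split of 34/26 or worse has a probability of about 0.37. Take assumed variances of 12 and 6, with the more variable arm at 26:
- separate variances: 12/26 + 6/34 = 0.638;
- pooled: (25×12 + 33×6)/58 × (1/26 + 1/34) = 8.586 × 0.0679 = 0.583;
- √(0.638/0.583) = 1.046, or about 5% wider once the covariate is estimated.

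In that setting the pooled t interval is too narrow (simulated coverage 93.3–94.3%, against 93.7–94.7% for HC2). With the more variable arm larger, HC2 is about 4% narrower at r = 0.

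None of these figures applies to outcomes compared by chi-square.

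**The case against.** The strongest reply is that nothing here is an error. The tests are exploratory, the trial is a pilot, and preferring a covariate-adjusted model to a t-test is partly taste. The premise cannot be checked, because the survey items are not shown and one instrument name may cover two related forms. The correlation is unknown, and daily smoking at entry may leave little baseline variation. A shift from 0.517 to 0.498 SD would change no conclusion of the pilot. Much of the value lies in reporting a mean difference with its interval, which needs no adjustment.

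All of this stands as a limit on size and priority. It does not show that the adjustment would be wrong. The cost with equal arms is about 1% in width if the baseline is uninformative, and fixing the choice in advance prevents picking between adjusted and unadjusted results once both are seen.

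A reader might infer that the planned t-tests are invalid or biased. The documents do not support that: allocation is random, and simulated t-test coverage was close to 95% with 30 per arm.

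**Conclusion.** The point holds as an optional improvement in precision, conditional on both recall items being asked before randomisation. With 30 per arm and an assumed r of 0.2 to 0.3, the half-width falls from 0.517 SD to between 0.511 and 0.498, worth about 1 to 5 participants.

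Two stronger readings should be resisted:
- **A large gain.** At r = 0.5 the ratio is 0.75 × 1.018 = 0.763, and 60 would act like 79. Nothing in the documents supports a correlation that high, and the entry criterion and likely zeros point towards a smaller gain.
- **No primary outcome is touched.** Section 3.0 does list these endpoints as secondary. Section 11.0, however, can be read as placing preliminary cessation estimates among the primary outcomes, so that reassurance cannot be given without qualification.

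**What to change.** Check the survey form first. If both items are asked at baseline, add to Section 11.0:
- For each of the two numeric endpoints, fit a linear model of the week-12 value on arm and the baseline value of the same measure.
- Use HC2 standard errors with a t reference on N−3 degrees of freedom, and report the adjusted mean difference and its 95% interval beside the unadjusted t-test result.
- State how a skipped baseline item is handled, for example by filling it with the overall (not by-arm) baseline mean. With 10% skipped, simulated coverage was 94.2–95.2%.
- If only one participant has a non-zero baseline value, that participant has leverage 1 and HC2 is undefined. If all values are zero, the baseline term cannot be fitted. In either case use the unadjusted result.

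If the items are not asked at baseline, report the unadjusted mean difference with its 95% interval.

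The cost is a look at the form and a few lines of text and code, with no new data. The statistical price is an interval about 1% wider if the baseline is not prognostic (3–4% with HC3), and about 5% wider than the pooled t interval in the 34/26 unequal-variance case above. In simulation the adjusted estimate also had a small-sample bias of at most 0.036 on a difference of 1.00 attempts and 0.22 on 7.70 days, or about 4% and 3%.
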